#### 9.8 Quality Control

Good clinical data management is a high priority at the DSRU. A number of strategies exist to minimise biased study results. The DSRU has a set of rules and processes associated with the conduct of pharmacoepidemiological studies. Data quality is assured through a number of methods based on error-prevention, data monitoring, data cleaning and documentation. These include:

- Operator training
- Vigilance of operators at the various stages of processing
- On screen validation during data entry
- $\circ$   $\;$  Adoption of and adherence to study-specific data coding conventions
- Coding review meetings
- Code list and algorithms

- Double entry (random sample of 10% of questionnaires), error reporting and correction of discrepancies between the entries by quality assurance staff
- Coding of questionnaires are randomly reviewed by a quality assurance assessor
- Routine data cleaning to screen for errors, missing values and extreme values, and diagnose their cause; this being supported by bespoke software with objective, standardised logical checks and undertaken by the DSRU data manager or allocated staff
- Relevant maintenance of reference tables
- Pilot testing of study documentation

#### 9.9 Limitations of the Research Methods

- Possible delay in new user cohort accrual if adoption by secondary care hospital trusts and specialists is low.
- Since this is an observational epidemiological study, we recognise several 0 potential sources of bias. The most important is selection bias and the possibility that the cohorts will not be representative of the population for who anticoagulation is clinically desirable for ACS. Because of the nature of patient recruitment, bias in recruitment may be introduced by some participating specialists through awareness of some form of remuneration (regardless of how and when payment is made). The same number of patients treated with other treatment combinations for ACS will be collected to explore factors which may contribute to selection bias. We have deviated from the new user design for antiplatelet treatment. This was done to allow inclusion of patients who might already be antiplatelet users for primary or secondary prevention of ACS. Although this deviation may have implications for the bleeding risk because these patients may have a higher baseline risk at start of rivaroxaban use, this allows inclusion of rivaroxaban patients that would otherwise be excluded based on a new user design.
- Knowledge of which patients will be participating may affect the noninterventional nature of observational research, however this will probably be minimised by the fact that they are members of broad research networks within the UK healthcare system. It is also possible that specialists who participate in the study will be a self-selected group, but we do not believe that this selection bias will affect the types or number of events experienced and reported by a patient after treatment has been initiated.
- Confounding by indication is a form of selection bias where the disease that forms the indication being treated (irrespective of severity) is not only associated with treatment but also an independent risk factor for selected outcomes (events of interest) in patients not exposed to antithrombotic agents. This needs to be examined since such channelling may result in apparent association of increased

risk of such events in this population. It may be introduced through prescribing of treatment based on certain characteristics of a patient. For this study, patients for whom prior alternative treatment was poorly tolerated or ineffective may be selectively prescribed the new treatment.

- $\circ$   $\,$  Confounding by severity is possible and needs to be accounted for.
- Under- and mis- reporting of outcomes is possible; specialist HCPs' notes may be incomplete with regard to medical history and non-cardiovascular related outcomes of interest associated with current treatment. The two-phase data capture approach could facilitate compliance with data reporting as well as spreading workload for specialist HCPs. By obtaining information from all patients GPs and access to primary medical charts, under ascertainment of outcomes can be minimised. In contrast, over-recording of health related events in the period following the administration of the baseline questionnaire are possible due to increased specialist HCP attention to special populations of interest (patients with concomitant complications) as detailed in the questionnaire, however since information is being abstracted from medical charts such bias is unlikely. However, this is likely to be similar in the contextual cohort.
- Regarding the definition of bleeding, in this study case definitions are based on acceptable agreed clinical standards and aim to address specific regulatory questions in the context of the risk management plan for the product.
- Immortal time bias is possible arising from misclassification of exposure to the study drug.
- With this patient population, patient attrition and loss to follow-up may introduce selection bias, however, the relatively short period of observation should mitigate this possibility at least to some extent.
- Misclassification bias will be minimised by well defined outcome and follow-up of medically important events. Patients with selected events of interest will be followed-up with regard to co-prescribed medicines and concurrent illness. Events that represent features of the respective indications will be taken into account when safety signals are investigated (i.e. confounding by indication).
- Furthermore unidentified poor adherence may also lead to misclassification of exposure. However, as with many observational studies, the degree of patient compliance in taking the prescribed medication cannot be ascertained. Whilst it is not possible to be sure the patient used the medication, it is almost certain that the patient received it since starting treatment is required for study participation. This is unlikely to be significant in this patient population, and for the 12 week period of observation.
- The potential exists for misclassification of mild renal failure since severe forms of renal failure will be more readily identified. However, to limit this, specific information about renal function (e.g. eGFR and serum creatinine levels) will be

collected during the course of the observation period to provide details of renal function.

### 9.10 Other aspects

Not applicable

## **10** Protection of Human Subjects

### **10.1** Good pharmacovigilance practices

Studies conducted by the DSRU are undertaken according to national and international guidelines for ethical conduct of research involving human subjects (20-23). Following the principles of good pharmacovigilance practice (17;24;25), a full protocol is written for each study to monitor and research the safety of medicines.

## 10.2 Confidentiality

Patient information security is assured through strict measures as laid out in the DSRU Information Governance Policy.

## 10.3 Patient consent

For this cohort study, ethics approval via IRAS (integrated research application system) in the UK will be required. Participating specialist HCPs will be asked to provide patients with documentation (with a unique study reference code). Patient study documentation will include a patient information sheet about the study which will describe that their primary and secondary care medical charts will be accessed during the time-frame of active study data collection by the HCP and/or DSRU research staff in order to extract exposure and outcome data relevant to the 12 week observation period. It will also provide contact details of the DSRU study team if they have any questions.

Specialist HCPs will provide patients with a consent form so that patients can consider and give consent for their participation within this project. The consent form will stress confidentiality, that no specific details of their treatment will be released to external parties, that the patient may withdraw consent at any time by contacting either the specialist HCP or the DSRU study research team directly, and that the patient will not be asked to attend clinics more than usual or undergo any additional treatment or questioning. The consent form will also request information to be provided on patient ethnicity, current marital status, current employment status, smoking and alcohol use. This is optional and will be used to inform on representativeness of study cohort. Three

<sup>1 The exception will be if a female patient becomes pregnant, the outcome of the birth will be requested.

signed copies are required. Those patients who wish to inform the DSRU immediately of their decision will give the signed consent form to the specialist HCP. They in turn will send the original to the DSRU, retain one copy for their records and issue a copy to the patient.

For those patients who wish to have a further opportunity to reflect on their participation, the specialist HCP will ask the patient to complete a 'consent to contact' form, which will enable DSRU study research staff to contact the patient through their preferred route of contact (surface post, email, or telephone) after a period of at least two days to obtain consent. This will be the only point at which DSRU research staff will contact the eligible patients directly. If the patient agrees to participate, they will sign the consent form , retain a copy and send the original and one further copy via surface mail to the DSRU study coordinating centre, or, if preferred, to the specialist HCP (who will then submit the original form to the DSRU). Receipt of the signed consent to contact form or the fully completed consent form (if patient provides immediate consent) by the DSRU study team should be within four weeks after index date, if possible.

In addition, within the same time frame, the specialist HCP will be asked to summarise selected data from the medical charts (non-clinical reasons for prescribing, demographic and treatment details) using a simple questionnaire (anonymised using the patient's allocated study reference number) and send these data to the DSRU coordinating centre either through a secure electronic website, or via surface mail.

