<sup>1 Non-clinical reasons for prescribing include: factors associated with accumulation of authoritative evidence (formulary committee approval; recommendation from NICE; expert committee guidelines); and behavioural factors (personal expertise in treating condition; history of clinical success with similar treatments).

<sup>2 http://www.nice.org.uk/media/6F2/BD/AcuteCoronarySyndromeRivaroxabanDraftScope.pdf

identified based on different clinical needs of subgroups (the contextual comparator will be a single group consisting of all possible standard of care combinations combined) :

- Clopidogrel in combination with aspirin
- Ticagrelor in combination with aspirin
- Prasugrel in combination with aspirin
- Additional dual antiplatelet therapies (not specified above)

After the pharmacotherapeutic treatment decision has been made by the clinician, such that the most appropriate treatment based on clinical need is prescribed, a patient will be invited to participate in the study and consent obtained for access to information from secondary care medical charts and general practice primary care medical charts via the GP. Participants will be invited to take part in the study by a member of the research or clinical team. This will usually be a research nurse, or practitioner, or clinical researcher or treating clinician (junior doctor or consultant).

To allow inclusion of patients with a previous history of ACS or other co-morbidities requiring antiplatelet treatment, a modified version of the new user design will be used in this study. The new user design will be used for the anticoagulant treatment and is defined as no use of oral anticoagulants including rivaroxaban within the 6 months prior to index date in both cohorts. In the rivaroxaban cohort, naïve users are defined as those who never used any oral anticoagulants in the past and they will be distinguished from non-naïve users in the analysis. The new user design will not be applied to antiplatelet treatments; ongoing antiplatelet treatment will be allowed in both cohorts and presented by naivety status.

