#### 9.2.3 Patient Inclusion Criteria

Since this is an observational cohort study conducted in a naturalistic setting, open patient entry criteria apply to maximise external validity. The inclusion criteria are:

- Age 18 years or above
- Patients newly prescribed rivaroxaban in any combination with standard oral antiplatelet therapy for the indication of secondary prevention in patients after ACS
- Patients prescribed dual antiplatelet therapy (contextual cohort) for the indication of secondary prevention after ACS
- Patients have provided signed, informed consent

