#### 9.2.5 Evaluable cohort

Evaluable patients are those patients who have provided consent and for whom analysable clinical data has been provided in the data collection questionnaires. Evaluable patients for whom the 12 week survey questionnaire (from both specialist HCP and GP) is returned blank (contain no clinical information) or has not been returned will Version 7 Date: 30/08/2017

only be included for analysis of secondary and exploratory objectives, where appropriate.

Consented patients will not be considered evaluable if the specialist HCP reports that the patient did not take either combination therapies. If there is evidence to suggest duplication of patients, either through inadvertent duplication between different prescribers within the same clinical setting, or if a patient was switched from one combination therapy to the other, then the records identified will be considered for inclusion on a case by case basis by the advisory committee.

Patients will be automatically withdrawn if the patient or specialist HCP provides informed written or verbal notification that they no longer wish to participate at any stage of the study.

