#### Part 2: Recruitment of eligible patients initiated with the study drug combination under clinical care of participating specialist HCPs.

For all eligible consented patients invited to participate, the specialist HCP or a member of their clinical team, will be asked to record anonymously (using the study reference number provided on patient study documentation) a summary of non-clinical reasons for prescribing, demography (age and sex), indication and selected treatment details onto a simple questionnaire and submit these data to the DSRU coordinating centre either through a secure online website, or via surface mail. Date of recruitment into the study Version 7 Date: 30/08/2017

will also be recorded by the specialist HCP, if known, or, retrospectively once the consent form is obtained, by the DSRU research staff. The unique study reference number allocated to each patient will be used for study audit and data management processes.

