#### 9.7.1 To quantify the cumulative incidence (risk and rate) of major bleeding according to the TIMI classification of non-CABG Related Bleeding (Table 1) occurring in the 12 week observation period, overall and stratified by intracranial, gastrointestinal and urogenital bleeding sites.

The following relates to Section 8.2 primary objective and relates to haemorrhage within gastrointestinal and urogenital organ sites (which meets the criteria for a TIMI major non CABG related bleed) and all intracranial sites (as defined in Table 1). This time to event analysis will be performed separately for the rivaroxaban exposed cohort and the contextual cohort, as defined according to exposure at index (date antiplatelet therapy was prescribed as part of the acute management of the ACS).

<sup>1 In the event of a change in treatment resulting in a switch in treatment group, person-time contributed will be censored at the time of switching, thus analysis will not be 'intention to treat' as this is an observational study.

For each cohort, for whom acute management of ACS applies, the numerator for this analysis will comprise of adjudicated incident major bleeding events (overall and stratified by intracranial, gastrointestinal and urogenital bleeding sites) defined according to primary objective that were reported during the 12 week observation period post index date. These adjudicated events will have been reviewed by an expert panel using all available information from SCEM questionnaires, follow-up and any additional documentation. Patients for whom events were misreported will be excluded from the analysis (events will be excluded, but denominator data will still be included); patients for whom events were misclassified will be reclassified as appropriate. In addition, for each cohort, for the three organ sites specified in the primary outcome, counts of each of the individual components of the TIMI major non CABG related bleeding criteria will be summarised. Where an individual has one or more criterion for an individual organ site of interest, counts will also be summarised – in such individuals the first report will be regarded as the incident event. Since SCEM data are right censored, the cumulative incidence (risk and rate) of the primary outcomes reported during treatment within the 12 week observation period will be calculated using survival analysis methodology.

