For each individual case, relevant person-time will be estimated according to duration of observation up to event date. For each individual non-case, relevant person-time will estimated by either exit date – index date; or censor date – index date; or stop date (+ 2 days ) – index date. For each cohort separately, a semi-parametric time-dependent Cox Proportional Hazards regression model will be used to estimate the crude cumulative incidence over the 12 week observation period.

Non-parametric Kaplan-Meier plots will be presented to describe time-to event as well as smoothed estimates of the empirical hazard function to describe how the crude baseline risk of the event changes over time.

Estimates of the hazard function will also be modelled to determine whether the baseline hazard (risk) of the event increases or decreases with time. A constant hazard over time may be consistent with a background (not caused by the drug) event rate, whereas a non-constant hazard over time may be an indicator of a drug-event relationship. The null hypothesis that the hazard rate of the selected event in patients will be constant during the 12 week period following the start of treatment will be tested

<sup>1 This excludes patients prescribed rivaroxaban 2.5mg for non-ACS related indications

<sup>2 Censor date = date of loss to follow-up

<sup>3 2 days allocated to person-time to account for half-life of drug

Version 7 Date: 30/08/2017

by fitting a parametric time to event model (e.g. Weibull). Such models have a shape parameter that indicates whether the hazard is significantly increasing or decreasing over time. At least five reports of an event are deemed necessary for modelling purposes.

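### Person-time in the primary analysis starts at the antiplatelet index date, although a patient can enter only by consenting later, so the earliest fatal or incapacitating bleeds go unseen

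*Protocol*

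**What the plan says.** **Entry.** Among the inclusion criteria in Protocol 9.2.3 is "Patients have provided signed, informed consent". Section 9.2.5 carries this into the analysis set: "Evaluable patients are those patients who have provided consent". By section 9.1, once the regimen has been chosen, "a patient will be invited to participate in the study and consent obtained for access to information".

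**Timing of consent.** Section 10.3 lets a patient sign at once. A patient who wants time to reflect completes a consent-to-contact form and is approached "after a period of at least two days to obtain consent". Receipt of either form "by the DSRU study team should be within four weeks after index date, if possible". Under 9.4.1 Part 2, the recruitment date "will also be recorded by the specialist HCP, if known", and otherwise study staff complete it retrospectively from the consent form.

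**Time zero.** Section 9.7.1 groups patients "as defined according to exposure at index (date antiplatelet therapy was prescribed as part of the acute management of the ACS", and 9.1 starts observation on the same date. For non-cases, "relevant person-time will estimated by either exit date – index date", or the censor or stop date minus the index date. Section 9.1 also says the index date will depend on the prescribing patterns seen, but no section moves it to consent.

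**What is already planned.** One sensitivity analysis in 9.7.1 adds a time-varying indicator for exposure before and after the first rivaroxaban or standard-care prescription. Section 9.9 attributes immortal time to misclassified exposure. Its other selection-bias remarks cover representativeness, recruiter behaviour and loss to follow-up.

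**The concern.** A patient who dies of a bleed before signing, or loses capacity through an intracranial haemorrhage, does not enter on the rules shown and adds neither an event nor time. Patients who do enter were, by construction, alive and able to consent on the day they signed. Their time from index to consent is nevertheless counted as fully at risk. This is left truncation without a delayed-entry correction.

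The events lost are the gravest ones. Table 1 lists fatal bleeding and symptomatic intracranial haemorrhage as TIMI major criteria, and intracranial bleeding is one of the three named sites in the primary objective. The bias is downward in a study whose purpose is to quantify harm.

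The hazard shape is exposed too. Section 9.7.1 treats a non-constant hazard as a possible sign of a drug-event relationship. A deficit of early events can make a constant hazard look as if it rises, or mask an early peak.

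Section 9.2.2 says the new-user design avoids survivorship bias associated with existing users. Requiring consent after time zero brings a related form of it back.

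**Working it through.** **Inputs from Protocol 9.5.** Expected 12-week incidence p = 0.5% (intracranial 0.1%, gastrointestinal 0.3%, urogenital 0.1%), precision ±0.4%, 1193 patients per cohort.

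**The plan's own figure.** n = 1.96² × 0.005 × 0.995 / 0.004² = 1194.5, against the stated 1193. A finite-population correction with N = 1,000,000 (inferred, not stated) gives 1193.0. The figure reproduces.

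**Expected events.** 1193 × 0.005 = 5.97, of which intracranial 1193 × 0.001 = 1.19, and gastrointestinal plus urogenital 1193 × 0.004 = 4.77.

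**Effect on incidence.** Let f be the share of 12-week bleeds falling before consent and m the share of those that prevent consent. With consent at week w and Weibull shape k, f = (w/12)^k. The incidence among those who enter is p(1 − fm)/(1 − pfm).

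The documents give neither the consent delays nor m, so w, k and m are all assumptions. The value m = 20% uses the intracranial share (0.1/0.5) as a stand-in.

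| Consent at | Hazard | f | m = 20% | m = 50% | m = 100% |
|---|---|---|---|---|---|
| 2 days | constant | 0.024 | 0.498% | 0.494% | 0.488% |
| 1 week | constant | 0.083 | 0.492% | 0.479% | 0.459% |
| 2 weeks | constant | 0.167 | 0.483% | 0.459% | 0.417% |
| 4 weeks | constant | 0.333 | 0.467% | 0.417% | 0.334% |
| 4 weeks | front-loaded, k = 0.5 | 0.577 | 0.443% | 0.356% | 0.212% |

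Worked cell (4 weeks, constant hazard, m = 20%): 0.005 × (1 − 0.0667)/(1 − 0.000333) = 0.467%.

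**Intracranial events alone.** If every pre-consent intracranial bleed prevented consent, the expected loss under a constant hazard is 1.19 × 7/84 = 0.10 event (consent at day 7) or 1.19 × 28/84 = 0.40 (day 28). With k = 0.5 it is 0.34 or 0.69. Fatal bleeds at other sites would add to this; the documents give no share.

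**Effect on the hazard shape.** For rare events with follow-up to 12 weeks, the Weibull shape estimate tends to 1/E[ln(12/t)], which is 1 when the hazard is constant. Removing a share m of the events in the first four weeks gives E = (1 − m × 0.6995)/(1 − m/3), where 0.6995 = (1/3)(1 + ln 3).

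- m = 20%: E = 0.922, shape 1.09
- m = 50%: E = 0.780, shape 1.28
- m = 100%: E = 0.451, shape 2.22

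A simulation of four million patients gave 1.08, 1.26 and 2.21. The relative standard error of the shape is about 1/√d, or 1/√5.97 = 0.41, so with about six events only the extreme case would stand out from noise.

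**Reaching five events.** Section 9.7.1 requires at least five reports for modelling. The Poisson probability of five or more is 0.71 at 5.97 expected events, 0.65 at 5.57 (m = 20%, four weeks) and 0.37 at 3.98 (m = 100%).

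**What delayed entry does.** In the worst case (constant hazard, consent at week 4, every earlier bleed lost), 3.98 events are seen. Counted from index the rate is 3.98/(1193 × 12) = 0.278 per 1000 patient-weeks. Counted from consent it is 3.98/(1193 × 8) = 0.417, against a true 0.418.

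**The case against.** The strongest reply is that the effect is probably small. Patients may sign immediately, the charts are abstracted back to index, and every early bleed that leaves the patient able to consent is still counted. In the 20%, four-week case the incidence falls by 0.033 percentage points, about 8% of the ±0.4-point precision (0.033/0.4). That stands, and it limits the weight of the point.

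Three stronger readings are tempting, and the documents do not support them.

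- **Four weeks as the consent delay.** Section 10.3 sets a soft target for receipt of a form, which may be only the consent-to-contact form. Actual consent may come later than that, or on the first day. It is neither a ceiling nor a typical delay.
- **A loss of one or two events out of six, that is 17–33%.** Nothing in the documents yields that number. Early risk concentrated before consent is likewise an assumption; 9.7.1 leaves the hazard shape to be tested.
- **A bias that differs between cohorts.** Rivaroxaban may start after the antiplatelet index, so consent could come later in that cohort. However, 9.2.2 prescribes a corresponding procedure for the contextual cohort, the primary analysis is run separately in each, and no figures on consent timing are given.

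One might also argue that delayed entry should be the main analysis. With consent at day 28 and a constant hazard, that would drop about 4.77/3 = 1.6 observed gastrointestinal and urogenital bleeds to address an expected intracranial loss of about 0.4, and leave about 4 events, below the five needed for modelling. Keeping the index-based analysis as main is defensible.

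Finally, consent pages were removed from the text reviewed, so a consultee or proxy route described there cannot be excluded. Sections 9.2.3, 9.2.5 and 10.3 mention none.

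**Conclusion.** The point holds as a modest, systematic downward bias that the protocol neither names nor examines. It follows from two rules the protocol fixes itself: consent as a condition of entry, and person-time measured from an earlier date. It is therefore not a detail left to the statistical analysis plan. The exposure-status sensitivity analysis cannot detect it, because patients lost before consent are absent from the data whatever exposure coding is used.

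The size cannot be fixed from the documents. Under a constant hazard the assumed range runs from almost nothing (0.498%) to 0.334% if every bleed in a four-week window prevented consent; 0.47% is a reasonable illustration, not an estimate. A front-loaded hazard makes it worse. The effect on overall incidence is likely to be small against the planned precision. It matters more for the intracranial stratum, for fatal bleeds and for any reading of the early hazard.

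All of this assumes that no proxy consent route exists and that index stays at the antiplatelet date. A later index date would shorten the gap to consent without necessarily closing it.

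**What to change.** 1. In 9.7.1, keep the index-based analysis as main. Add a left-truncated sensitivity analysis of the primary incidence and of the hazard-shape model: same time scale from index, with each patient joining the risk set at the recorded recruitment or consent date.
2. Report the index-to-consent interval (median, quartiles, maximum) for each cohort. Short intervals would show that the bias is trivial.
3. List first major bleeds that occurred between index and consent, by site and cohort.
4. In 9.9, state that bleeds which prevent consent are not observed, that the direction is downward, and that this is separate from exposure misclassification.

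**Cost.** One entry-time variable, a second run of models already planned, and one descriptive table. The sensitivity analysis will have fewer events and thin early risk sets, so it may be too sparse for the shape model. The recruitment date is sometimes completed retrospectively, so the report should say how many dates were filled in that way.
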